To assess how COVID-19 lockdown has changed the dietary habits of participants enrolled in this study. In order to collect this information, we will ask for the participant to complete an online 3-day food record. This part of the study is non-invasive and there will be no in-person contact.

Aim 5 – Exploratory

To assess whether the colonic fermentation modulates gluconeogenesis. Hypothesis: Glucose fermentation induced by lactulose is associated with a drop in gluconeogenesis. Subjects will assume 3ml/ Kg of body water of D2O in three doses *per os* the night before the study and at 7:30 AM they will consume 20g of lactulose. Blood draws will be taken every hour until 8:00 PM. The total blood to be drawn is about 150 ml. The subjects will be allowed to drink during the study, a meal will be served at the end of the study.

We will also collect the breath hourly hydrogen breath test during the study to assess colonic fermentation by measuring hydrogen in the breath. Subjects blow into a small box to collect the breath. There are no risks related to this test.

Aim 6 - Measurement of TCA cycle in vivo in the brain and in the liver by using Deuterium metabolic imaging.

Deuterium metabolic imaging (DMI) is a simple MR-based technique to map metabolism with high temporal and/or spatial resolution. The metabolic fate of deuterated substrates, including glucose and acetate, can be monitored with deuterium MR methods. Recent preliminary data obtained with this protocol suggest that youth with obesity have higher TCA cycle compounds in plasma than lean. This is probably due to an increased metabolic rate related to insulin resistance. To determine if changes observed in plasma mirror metabolic changes in the tissue (brain and liver), we will use a technique that combines stable isotopes and MRI. To measure TCA cycle in the brain we will use 6,6-2H₂-glucose, a compound that has been used for many years in clamp studies, while to measure TCA cycle in the liver we will use D3-Acetate, the compound that we are currently using to measure acetate production (Aim 1 and 3).

TCA cycle measurement in the brain.

To measure TCA cycle measurement in the brain we will infuse 6,6-2H₂-glucose for 2 hours and we will detect the changes in TCA derived compounds in the brain during the infusion. A total of 50 ml of blood will be obtained during this study.

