Statistical Plan for Aim 4. Since aim 4 is an exploratory study for which we do not have preliminary data it is difficult to determine the sample size needed to detect differences in dietary changes during the lockdown. The main outcome for this arm of the study will be changes in Kcal intake. Secondary aims will be changes in the intake of macro- and micro nutrients. This arm of the study will be limited to ~40 subjects for which we have pre-lockdown dietary information. Data analysis. Descriptive statistics, such as means and standard deviations (or medians and interquartile range, IQR), counts and percent will be used to describe characteristics of subjects before the study. A paired non-parametric test will be used to compare the outcomes before and after the lockdown within groups, while a general linear model will be used to compare changes in the outcomes between groups. Statistical significance will be established at the two-sided alpha of 0.05. Analyses will be performed using SAS 9.4 (Cary, NC), Prism and R statistical software.

Statistical Plan for Aim 5. In our preliminary data, we observed changes in glucose of 89.3 mg/dl at baseline and 78.8 mg/dl at the end of the study (7 hours after lactulose ingestion). Given the following: 1) a power of 95%, 2) a standard deviation of 8.0, and 3) a one-sided 0.05 significance level a sample size of 14 subjects will be required to detect the above shown difference in percent changes with 95% power at the one-sided 0.05 significance level within each group. Since we will explore also whether percent changes in gluconeogenesis are different between lean we will recruit about 20 subjects per group. Statistical Analyses: Median and interquartile ranges will be calculated. The primary outcome will be gluconeogenesis changes after lactulose ingestion within groups (lean and obese). Non-parametric one sided test will be used to compare gluconeogenesis between baseline and the end of the study. We will also explore the possibility that changes in gluconeogenesis might occur to different extents between the groups, therefore we will compare percent changes gluconeogenesis between the groups using a general linear model using basal gluconeogenesis as covariate.

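### Aim 5 (exploratory): an uncontrolled baseline-to-end test cannot separate a fermentation effect from drift over the visit, and the breath hydrogen collected is not used

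*Combined protocol and SAP*

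**What the plan says.** Section I, item 4 (Research Plan), Aim 5, is headed exploratory. Its hypothesis is: "Glucose fermentation induced by lactulose is associated with a drop in gluconeogenesis". Subjects take labelled water by mouth "the night before the study and at 7:30 AM they will consume 20g of lactulose". Sampling follows: "Blood draws will be taken every hour until 8:00 PM". On feeding: "The subjects will be allowed to drink during the study, a meal will be served at the end of the study". On the measurement of fermentation: "We will also collect the breath hourly hydrogen breath test during the study to assess colonic fermentation by measuring hydrogen in the breath". No placebo, no-lactulose day or time control is described for this aim.

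Section I, item 13 (Statistical Considerations), Statistical Plan for Aim 5, sets the outcome: "The primary outcome will be gluconeogenesis changes after lactulose ingestion within groups (lean and obese". The test is: "Non-parametric one sided test will be used to compare gluconeogenesis between baseline and the end of the study". A further exploratory model will "compare percent changes gluconeogenesis between the groups using a general linear model using basal gluconeogenesis as covariate". Breath hydrogen does not appear in the Aim 5 plan.

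The sizing uses plasma glucose: 89.3 mg/dl at baseline and 78.8 mg/dl at the end of the preliminary study, 7 hours after lactulose, with an SD of 8.0. It gives 14 subjects for 95% power at one-sided 0.05 within each group, and about 20 per group are to be recruited.

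**The concern.** The question is about an exposure, but the primary analysis contrasts two times in people who are all exposed. Whatever several more hours without a meal do to gluconeogenesis is added to whatever lactulose does, and the test sees only the sum. A significant fall therefore cannot be credited to fermentation, and a null result cannot rule out an effect that drift has offset. The preliminary fall in glucose is also presented without a comparator, so it does not show how much of the 10.5 mg/dl was drift.

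The protocol already collects an hourly measure of fermentation that could tie the change to the exposure. Aim 2, in the same item 13, takes that route: it regresses the change in de novo lipogenesis on the change in total SCFA. Aim 3 has a control-diet period. Aim 5 has neither.

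**Working it through.** **1. The planned sample size.** Difference = 89.3 − 78.8 = 10.5 mg/dl (10.5/89.3 = 11.8% of baseline). SD = 8.0, one-sided 0.05, 95% power, so both normal quantiles are 1.645.

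- Two-sample formula: n = 2 × [(1.645 + 1.645) × 8.0/10.5]² = 12.56, so 13. The t version gives 13.3, so 14. This matches the plan's figure.
- Paired, with 8.0 as the SD of the within-subject change: n = [(1.645 + 1.645) × 8.0/10.5]² = 6.28, so 7. The t version gives 8. This does not match.
- Paired, with 8.0 as the SD of a level and no within-subject correlation: SD of change = 8.0 × √2 = 11.3, n = 12.56 (z) or 14.04 (t). This matches to rounding.

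The plan does not say which SD the 8.0 is, so both 8.0 and 11.3 are carried forward.

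**2. What the test estimates.** For subject i, observed change = lactulose effect + drift + error. With lactulose given to everyone, the mean change identifies only the sum of the first two terms. In the lean-versus-obese model, drift common to both groups cancels, but so does any lactulose effect common to both. Drift that differs by group would look like a group difference in response.

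**3. Size of the problem.** Simulated studies with n = 20, normally distributed changes, no lactulose effect, and a one-sided Wilcoxon signed-rank test for a fall at 0.05. Ranges are over repeated runs. The drift values are assumptions.

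| Assumed drift | SD of change 8.0 | SD of change 11.3 |
|---|---|---|
| none | about 5% | about 5% |
| down 2 | 27–28% | 18–19% |
| down 4 | 67–68% | 43–44% |
| down 6 | 92–93% | 72–73% |
| up 2, 4 or 6 | 0–1% | 0–1% |

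Cross-check by one-sided paired t power, as fractions of the 10.5 difference: a downward drift of 10% (1.05) gives 14% (SD 8.0) or 11% (SD 11.3); 25% (2.6) gives 41% or 26%; 50% (5.25) gives 88% or 64%.

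**4. Masking.** By the same calculation, a real fall of 10.5 with no drift is detected in over 99.9% (SD 8.0) or 99% (SD 11.3) of studies. An upward drift of 5.25 leaves a net fall of 10.5 − 5.25 = 5.25, and detection drops to 88% or 64%.

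**5. The end time.** 7:30 AM to 8:00 PM is 12.5 hours in the Research Plan. The Statistical Plan describes the end of the preliminary study as 7 hours after lactulose. The structure in step 2 is the same at either time, but the amount of drift need not be.

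**6. What a breath-hydrogen analysis could detect.** Fisher z, two-sided 0.05, 80% power, 40 subjects: r = tanh[(1.960 + 0.842)/√37] = 0.43. With two covariates, √35 replaces √37 and r = 0.44.

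**The case against.** The strongest reply is that Aim 5 is labelled exploratory and its hypothesis speaks of association, so a before-after description may be all that is intended. That stands as a reason to grade the point modestly. It does not remove the point, because the stated aim is whether fermentation modulates gluconeogenesis, and a before-after test is not an association analysis.

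A second reply is that breath hydrogen does not cure the defect. Everyone takes the same 20 g at the same time, so in a model with hour as a factor the average hydrogen curve is absorbed. Only differences between subjects, or in individual timing, remain. These are observational and may reflect other traits. This also stands, and it is why the analysis should be added and labelled as an association rather than made the sole primary analysis.

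Three stronger readings are tempting, and the documents do not support them:

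- A reader might infer that any drift would be taken for an effect. The test is one-sided for a fall, so upward drift is not declared an effect; it hides one.
- A reader might infer that subjects certainly go 12.5 further hours unfed. The two Aim 5 texts imply different end times, drinks are allowed, and their content is not stated.
- A reader might infer that the exposure is wholly absent from the analysis. The hypothesis concerns fermentation induced by lactulose, and the outcome is change after lactulose. What is missing is the measured degree of fermentation and any comparison without lactulose.

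**Conclusion.** The point holds for interpretation: as planned, Aim 5 can show that gluconeogenesis changed over the visit but not that fermentation changed it. Neither the primary test nor the lean-versus-obese model separates the two.

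The rejection rates above are conditional illustrations, not an error rate for this study. They rest on assumed drifts, on either of two readings of the SD, and on n = 20. The 8.0 is stated alongside plasma glucose, whereas the tested outcome is gluconeogenesis, so the drift units have no established scale for the actual endpoint. The documents give neither the direction nor the size of drift, and they do not show that the hypothesised fall is an artefact. Given the exploratory label, this is a worthwhile and inexpensive improvement rather than a fatal flaw.

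**What to change.** In the Statistical Plan for Aim 5:

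1. Keep the within-group test, but report it as change over the visit and do not attribute it to fermentation.
2. Add a pre-specified regression of each subject's change in gluconeogenesis on breath-hydrogen AUC over the same interval, with group and baseline gluconeogenesis as covariates. If gluconeogenesis is assayed serially, which the plan does not specify, a mixed model with hour as a categorical factor and breath hydrogen as a time-varying predictor can be used instead.
3. Base any statement about fermentation on that analysis, and call it an association.
4. Reconcile the end time point between the Research Plan and the Statistical Plan, and use the same interval for the change and the AUC.

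The cost is wording and a small amount of analysis on data already collected, with no added visit, sample or subject. The downside is that the evidence stays observational, and about 40 subjects give 80% power only for a correlation of about 0.43–0.44 or more, so a weaker association could well be missed.

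### Aim 5 hypothesises a drop in gluconeogenesis, but with D2O as the only tracer it can yield a fraction of glucose and not a rate, so a flat or rising result would not refute the hypothesis

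*Combined protocol and SAP*

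**What the plan says.** The relevant text is in two places in the combined protocol and SAP.

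- **Section I, item 4 (Research Plan), Aim 5 – Exploratory.** The hypothesis is "Glucose fermentation induced by lactulose is associated with a drop in gluconeogenesis". The tracer is "3ml/ Kg of body water of D2O in three doses", taken by mouth, and the timing is "the night before the study and at 7:30 AM they will consume 20g of lactulose". Sampling is described as "Blood draws will be taken every hour until 8:00 PM", with hourly breath hydrogen. No infusion of labelled glucose and no other measure of glucose production is listed. Labelled glucose is infused only in Aim 6, for the brain TCA cycle.
- **Section I, item 13 (Statistical Considerations), Statistical Plan for Aim 5.** The primary outcome is the within-group change in gluconeogenesis, and the test is stated as "Non-parametric one sided test will be used to compare gluconeogenesis between baseline and the end of the study". Percent changes are then compared between lean and obese, with the basal value as covariate. Neither section says whether gluconeogenesis means a fraction, a concentration or a rate. The sizing rests on "we observed changes in glucose of 89.3 mg/dl at baseline and 78.8 mg/dl at the end of the study", with a standard deviation of 8.0, 95% power and one-sided 0.05, giving 14 subjects per group. About 20 per group are to be recruited.

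**The concern.** A drop in gluconeogenesis is most naturally read as a fall in the amount of glucose made per unit of time. Deuterium from body water that is built into plasma glucose shows what share of the glucose was newly made. Turning that share into a rate needs glucose production, which Aim 5 does not measure.

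A share depends on its denominator as well as its numerator. If total production falls, the share can stay level or rise while gluconeogenesis itself falls. The test is one-sided for a drop, so a rise cannot be declared and a level share counts as no effect. A true hypothesis could therefore be reported as unsupported, or even as contradicted. The lean–obese comparison is open to the same problem if production changes by different amounts in the two groups.

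The power statement does not help, because it was worked out on a different variable.

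**Working it through.** **Inputs from the Statistical Plan for Aim 5:** glucose 89.3 mg/dl at baseline and 78.8 mg/dl at the end; SD 8.0 (the plan does not say whether this is the SD of a change); one-sided alpha 0.05; power 95%; 14 per group.

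**1. The plan's sample size.** The difference is 89.3 − 78.8 = 10.5 mg/dl.
- Two-sample normal formula: n = 2 × [8.0 × (1.645 + 1.645) / 10.5]² = 12.6, so 13 per group. The noncentral-t version gives 14 (power 95.9%), which is the plan's figure.
- Paired formula with 8.0 as the SD of the change: [8.0 × 3.290 / 10.5]² = 6.3, so 7 (normal) or 8 (t).
- Paired formula with SD of change 8.0 × √2, meaning no within-subject correlation: 13 (normal) or 15 (t).

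The figure of 14 therefore reproduces, but as a sizing for plasma glucose in mg/dl. No mean or SD for any gluconeogenesis measure enters it.

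**2. How a share responds.** Let glucose production fall by a proportion x and gluconeogenesis by y. Share = gluconeogenesis / production, so the relative change in share is (1 − y)/(1 − x) − 1.

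The preliminary fall in concentration is 10.5/89.3 = 11.8%. The documents give no production data. Taking x = 11.8% assumes that production falls in step with concentration. Other values of x show the range.

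| Fall in production (x) | Fall in gluconeogenesis (y) | Relative change in share |
|---|---|---|
| 0% | 11.8% | −11.8% |
| 5% | 11.8% | −7.1% |
| 11.8% | 0% | +13.3% (89.3/78.8 = 1.133) |
| 11.8% | 5% | +7.7% |
| 11.8% | 10% | +2.0% |
| 11.8% | 11.8% | 0.0% |
| 11.8% | 20% | −9.3% |
| 20% | 11.8% | +10.3% |

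The 13% relative rise does not depend on the basal share. Assumed shares of 40%, 50% and 60% become 45.3%, 56.7% and 68.0%.

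**3. What the one-sided test would show.** This is a simulated one-sided Wilcoxon signed-rank test with n = 20, a true fall in gluconeogenesis of 11.8%, and an assumed SD of the percent change in share of 9 to 15 points. The documents give no SD for this measure.

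| Fall in production | Power to show a drop in the share |
|---|---|
| 0% | 100% to 95% |
| 5% | 94% to 63% |
| 11.8% | about 5% (equal to alpha) |
| 20% | about 0% |

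**4. Is share × plasma glucose a safe replacement?** Suppose gluconeogenesis and production are both unchanged and clearance rises. The share stays at, say, 50%. The product goes from 0.50 × 89.3 = 44.7 to 0.50 × 78.8 = 39.4 mg/dl, a fall of 11.8% with no change in gluconeogenesis. When the share is stable, the product is plasma glucose rescaled.

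**The case against.** The strongest objection is that a fall in concentration is not a fall in production. The plan reports concentration only. If clearance rises and production holds, share and rate move together and the share tests the hypothesis well (first rows of both tables above). This stands. A reader might infer that the share must mislead whenever glucose falls. The documents do not support that, and the 13% is conditional on production falling with concentration.

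Second, the plan never says that the outcome is a rate, so it may always have meant the fraction. That is a fair reading, and it means the outcome is undefined rather than shown to be wrong. That D2O labelling of glucose yields a fraction is general knowledge of the method and is not stated in the documents. What the documents do show is that nothing listed for Aim 5 measures production.

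Third, one might infer that fraction × glucose should become the tested outcome. Step 4 argues against it: with a stable fraction it would tend to show the hypothesised drop simply because plasma glucose falls, and that fall is already in the preliminary data.

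Fourth, a reader might take the sizing as evidence that Aim 5 is underpowered for gluconeogenesis. That cannot be established, because no baseline fraction, production rate or SD for either is given.

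Finally, the aim is labelled exploratory. This limits the weight of the point but does not remove it: the aim has a directional hypothesis, a named primary outcome and a 95% power claim.

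**Conclusion.** The point holds in a conditional form. As listed, Aim 5 can yield fractional gluconeogenesis and cannot yield a rate, while its hypothesis and primary outcome are worded without that limit. If production falls by the 11.8% seen in preliminary glucose concentration, the fraction falls only when gluconeogenesis falls by more than 11.8%. It is flat at exactly 11.8% and rises for any smaller fall, by up to 13% relative when gluconeogenesis is unchanged. A flat or rising fraction would therefore not be evidence against the hypothesis.

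This rests on two things outside the documents: the general property of the D2O method, and the assumption that production follows concentration. Separately, and without any assumption, the 14-per-group calculation concerns plasma glucose and not the primary outcome. No corrected sample size can be given from the documents.

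**What to change.** In the Statistical Plan for Aim 5:

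- Define the tested outcome as fractional gluconeogenesis (% of plasma glucose), with its formula. Reword the Aim 5 hypothesis and planned conclusion to match, with no claim about the rate.
- State that a flat or rising fraction will not be read as evidence against a fall in gluconeogenesis, because glucose production is not measured.
- Report plasma glucose and fraction × plasma glucose at the same time points as supportive measures only. State that the product assumes unchanged glucose clearance and falls with plasma glucose even when gluconeogenesis does not change.
- State that the 14-per-group, 95% power figure applies to plasma glucose and not to the gluconeogenesis outcome.

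The cost is a change of wording and one multiplication per time point on blood already drawn, with no new procedure. The downside is a narrower claim and a little more analysis.

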Statistical plan for aim 6. Sample size was estimated with the clinicalcalc online software ([Sample Size Calculator \(clinicalcalc.com\)](https://www.clinicalcalc.com)). Since lactate serves as a precursor of TCA cycle, we based our power calculations on the lactate levels measured during the fasting state in 12 lean and 18 obese children. Based on the mean+/-SD of lactate levels in non-obese group of 0.78+/-0.22 and in the group with obesity 1.023 +/- 0.36, a sample size of 23 subjects per group (46) is needed for an alpha of 0.05 and a power of 95%. Statistical Analyses: Median and interquartile ranges will be calculated. The primary outcome will be TCA cycle after 6,6 D glucose ingestion during the steady state. Non-parametric two sided test will be used to compare TCA cycle between the groups.

SECTION II: RESEARCH INVOLVING DRUGS, BIOLOGICS, RADIOTRACERS, PLACEBOS AND DEVICES

If this section (or one of its parts, A or B) is not applicable, check off N/A and delete the rest of the section.

A. RADIOTRACERS N/A

B. DRUGS/BIOLOGICS N/A

Does the study do any of the following:

Specify the use of an approved drug or biologic?

Use an unapproved drug or biologic?

Use a food or dietary supplement to diagnose, cure, treat, or mitigate a disease or condition? No

This study uses:

13C inulin (labeled) (isotope)
deuterated SCFA/labeled acetate
Deuterium labeled water (heavy water D2O)
6,6-2H2-glucose (isotope)

Lactulose is a dietary supplement that is approved to treat constipation. We will use lactulose to stimulate production of short chain fatty acids by the gut flora.

Cold Isotopes:

FDA allows the use of cold isotopes in research without an IND when certain conditions apply (see below). Confirm that the following are true:

1. *The research is intended to obtain basic information regarding the metabolism (including kinetics, distribution, and localization) of a drug labeled with a cold isotope or regarding human physiology, pathophysiology, or biochemistry.*
2. *The research is not intended for immediate therapeutic, diagnostic, or preventive benefit to the study subject.*
3. *The dose to be administered is known not to cause any clinically detectable pharmacologic effect in humans based on clinical data from published literature or other valid human studies.*
4. *The quality of the cold isotope meets relevant quality standards.*

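### Aim 6 claims 95% power with 23 per group, but its own means and SDs give about 77% (about 74% for the planned non-parametric test)

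*Combined protocol and SAP*

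**What the plan says.** The paragraph headed Statistical plan for aim 6 (Section I, item 13) bases the sample size on "lactate levels measured during the fasting state in 12 lean and 18 obese children", because lactate is a precursor of the TCA cycle. The inputs are a "mean+/-SD of lactate levels in non-obese group of 0.78+/-0.22" and, "in the group with obesity 1.023 +/- 0.36". From these it concludes that "a sample size of 23 subjects per group (46) is needed for an alpha of 0.05 and a power of 95" per cent.

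The primary outcome is the TCA cycle measure at steady state. The analysis is specified as follows: "Non-parametric two sided test will be used to compare TCA cycle between the groups".

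The calculation was done with an online calculator. The paragraph does not give the formula or the SD that was entered, and it makes no allowance for dropout or unusable scans.

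**The concern.** Everything needed to check the sample size stands in one paragraph, and the result does not follow from it. The planned difference is 0.243 and the two SDs average about 0.3, so the standardised difference is about 0.8. At that size, 23 per group is roughly what 80% power requires, not 95%.

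Power tells a reader how much weight a null result can bear. If 95% is believed, a non-significant Aim 6 comparison counts as fairly strong evidence against a difference of the planned size. If the true figure is about 75%, it does not. Aim 6 is not labelled exploratory, as Aims 4 and 5 are in the Research Plan, and it has a named primary outcome and a formal sample-size justification. Its power statement will therefore be taken at face value.

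**Working it through.** **Inputs, all from the Aim 6 paragraph.** Means 0.78 and 1.023, so the difference is 0.243. SDs 0.22 and 0.36. Alpha 0.05, two-sided (from the planned test). Target power 95%. Stated size 23 per group, 1:1.

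**Sample size from both SDs (normal approximation).**

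n per group = (z for alpha + z for power)² × (SD₁² + SD₂²) / difference²

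- SD₁² + SD₂² = 0.0484 + 0.1296 = 0.1780
- difference² = 0.243² = 0.05905
- (1.960 + 1.645)² = 12.996
- n = 12.996 × 0.1780 / 0.05905 = 39.2, so 40 per group

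A t-test needs 41. In simulation, Mann-Whitney power is about 94.4% at 42 per group and 95.5% at 44 (normal data), so it needs about 43 to 44.

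**Power at the stated 23 per group.**

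- Standard error = √(0.1780 / 23) = 0.0880
- 0.243 / 0.0880 = 2.76, and 2.76 − 1.96 = 0.80, which gives 78.9% by the normal approximation
- t-test: 76.7% (Welch, noncentral t) or 77.1% (equal-variance t with the root-mean-square SD, 0.2983)
- Mann-Whitney, simulated: 74% to 75% with normal data, and 73% to 74% with lognormal data having the same means and SDs

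**Trying to reproduce 23 at 95%.** The document does not say how the SDs were combined, so each plausible choice was tried. Each cell gives normal approximation / t-test.

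| SD used | n per group for 95% power | Power at 23 per group |
|---|---|---|
| Root-mean-square of both, 0.2983 | 40 / 41 | 78.9% / 77.1% |
| Simple average, 0.29 | 38 / 39 | 81.1% / 79.4% |
| Weighted by the 12 and 18 children, 0.3126 | 44 / 44 | 75.1% / 73.2% |
| Obese SD only, 0.36 | 58 / 59 | 62.9% / 61.0% |
| Root-mean-square, one-sided test | 33 / 34 | 86.8% / 85.9% |
| Lean SD only, 0.22 | 22 / 23 | 96.3% / 95.6% |

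Only the last row returns the stated figure. It uses 0.22 for both groups and drops the 0.36 quoted in the same sentence. A less likely route to 23 is 80% power with the simple-average SD, which gives 23 by the normal approximation. With the root-mean-square SD, 80% power gives 23.7, so 24.

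**Difference detectable with 95% power at 23 per group.** Normal approximation: 3.605 × 0.0880 = 0.317. Welch t: about 0.33. Mann-Whitney: about 0.34, since 0.33 gives 93.9% in simulation.

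**The case against.** The arithmetic is not in dispute. Four points can be made about what it means.

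- **The inputs describe a proxy.** The difference and SDs are for fasting lactate, whereas the primary outcome is the TCA cycle measure. The documents give no SD or expected difference for that outcome, so Aim 6's true power is unknown and could be higher or lower. This stands. It does not make 95% follow from the stated inputs, but any restated power must name lactate as the variable.
- **Matching could help.** Item 6 (Subject Population) says the lean and obese groups are matched. If Aim 6 were analysed in pairs, and if the within-pair correlation were about 0.5 (an assumption; the documents give no value), a paired t-test on 23 pairs would have about 94% power. But the Aim 6 plan specifies a between-group test and mentions no pairing, so this does not support the stated figure.
- **The inputs are imprecise.** They come from 12 and 18 children, and the choice of pooling both SDs alone moves parametric power between about 73% and 81%. This is a reason to quote rounded values. No point in that range is near 95%.
- **Aim 6 is a mechanistic sub-study.** It is absent from the aims in the Statement of Purpose, and the error does not touch Aims 1 to 3. That limits the consequence to Aim 6.

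Which SD went into the calculator is an inference, because the plan does not say.

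**Conclusion.** The Aim 6 power statement is wrong as written. For the planned unpaired two-sided comparison at 0.05, no combination of the two quoted SDs gives 95% power with 23 per group, and even one-sided testing reaches only 86% to 87%. The risk of missing the planned lactate difference is about 23% by t-test and 26% by Mann-Whitney, against the 5% claimed. The stated size is short of the 95% target by about 18 per group (41 − 23) for a t-test and about 20 to 21 per group for Mann-Whitney (43 or 44 − 23).

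This takes the preliminary lactate means and SDs as true values, assumes roughly normal or lognormal data and complete data on all 46 subjects. Any loss of subjects or scans would lower the power further.

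**What to change.** Keep 23 per group and replace the power statement with one that follows from the inputs, for example:

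> Using fasting lactate as a proxy for the TCA cycle outcome (means 0.78 and 1.023, SDs 0.22 and 0.36), 23 per group gives about 77% power by t-test, or about 74% by the planned Mann-Whitney test, at two-sided 0.05. The difference detectable with 95% power is about 0.33 (t-test) or 0.34 (Mann-Whitney).

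The plan should also say which SD was entered in the calculator. This costs one sentence, a less favourable power figure and no additional participants.

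If the investigators want to hold the 95% target for the lactate proxy, the alternative is about 43 to 44 per group for the planned test. Whether that is feasible for the imaging and infusion visits is not documented, so it is a choice for them and not needed to correct the error.
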